##### 3.1.1 Administrative structure of the trial

Boehringer Ingelheim has appointed a Trial Clinical Monitor, responsible for coordinating all required activities, in order to

- manage the trial in accordance with applicable regulations and internal SOPs,
- direct the clinical trial team in the preparation, conduct, and reporting of the trial,
- order the materials as needed for the trial,
- ensure appropriate training and information of local clinical monitors (CML), Clinical Research Associates (CRAs), and Investigators of participating countries.

Data Management and Statistical Evaluation will be done by BI according to BI SOPs.

Tasks and functions assigned in order to organise, manage, and evaluate the trial will be defined according to BI SOPs. A list of responsible persons and relevant local information can be found in the ISF.

A Coordinating Investigator will be nominated and will be responsible to coordinate Investigators at different centres participating in this multicentre trial. Tasks and responsibilities will be defined in a contract. Relevant documentation on the participating (Principal) Investigators and other important participants, including their curricula vitae, will be filed in ISF.

### **3.2 DISCUSSION OF TRIAL DESIGN, INCLUDING THE CHOICE OF CONTROL GROUP(S)**

A randomized, double-masked placebo-controlled design is chosen for this trial in order to evaluate pharmacodynamics, safety, tolerability and PK of 100 mg b.i.d. of BI 1026706 in patients with mild vision loss due to center-involved DME. Because an efficacious therapy is available for patients with DME who experience at least moderate visual loss (defined as a 15 or more letter score decrease in visual acuity), this trial aims to treat DME patients with only mild vision loss in order to stabilize or even improve central macular edema early in the course of the disorder where it is a reasonable alternative to observe disease progression with the possibility of initiation of rescue treatment at any time during the study.

The study is a short clinical proof of mechanism trial, and given a rather slow progression of DME the duration of the study is considered sufficient to assess the primary outcome of change from baseline in comparison to placebo by SD-OCT in lesion morphology ([R15-5225](#)). The chosen primary outcome is objective with minimal time related effects expected and is therefore appropriate.

A placebo control arm was chosen for this trial in order to compare BI 1026706 and placebo regarding safety and tolerability in patients with DME, which is another important aim of the trial. The treatment period of 12 weeks is deemed adequate to evaluate safety and tolerability, and is covered by currently available 13 weeks toxicology data.

Approximately equal numbers of patients will be randomized to both treatment groups. Randomization will be stratified by previous treatment for DME into treatment naïve versus previously treated patients as this may have impact on the expected effects regarding the primary outcome.

There is the possibility of rescue treatment according to standard of care interventions in the case of significant worsening of clinical and PD parameters at all times during the study for both treatment arms, BI 1026706 and placebo.

### 3.3 SELECTION OF TRIAL POPULATION

A sufficient number of male and female patients with DM either type 1 or type 2 and center-involved DME with mild vision loss will be screened to ensure the randomization of 100 patients from around 44 study sites. The reason for conducting the study with many sites lies with the expected enrolment rate which might be low, as patients are only mildly affected and pure observation is a reasonable option before starting standard intravitreal injection therapy. To take account of the consistent evaluation of endpoints at all sites only prequalified study sites will participate, and SD-OCT images will be evaluated by an independent central reading center (CRC).

It is expected that around 2-3 patients will be randomised at each study site. If enrolment is delayed, additional sites may be recruited. Permission to enrol more than 15 patients per site must be obtained from the TCM at BI. This will only be allowed after a careful review of the enrolment status and of the site.

Screening of patients for this study is competitive across all countries within the study, i.e. screening for the study will stop at all sites when it is anticipated that a sufficient number of patients have been screened to yield the desired number of patients randomised to trial treatment. Investigators will be notified when sufficient patients have been screened and when screening is complete, and will not be allowed to recruit additional patients for the study. Patients who have completed Visit 1 procedures prior to notification of the termination of recruitment will be allowed to continue in the study, if they meet all entry criteria and they are able to follow the visit schedule specified in this Clinical Trial Protocol (CTP).

A screening log of all patients enrolled into the trial (i.e. who have signed informed consent) will be maintained in the ISF at the investigational site irrespective of whether they have been treated with investigational drug or not.

#### 3.3.1 Main diagnosis for trial entry

Patients with vision loss due to center-involved DME at the Screening visit are eligible for inclusion if they fulfil all of the inclusion criteria and none of the exclusion criteria. Only one study eye per subject may be enrolled. Ophthalmologic evidence of center-involved DME in the study eye needs to be confirmed by the CRC.

Please refer to [Section 8.3.1](#) (Source Documents) for the documentation requirements pertaining to the in- and exclusion criteria.

##### 3.3.1.1 Study eye criteria

The following procedure is to be applied for the selection of the study eye at baseline:

If only one eye meets all of the inclusion and none of exclusion criteria, this eye will qualify for the study eye;

- If both eyes in an individual patient meet all of the inclusion criteria and none of the exclusion criteria, the eye with the larger CSF thickness (CSFT) will qualify for the study

eye; the fellow eye will be examined only for safety reasons and will be not enrolled into the analysis of the primary endpoint;

- If both eligible eyes show the same size of CSFT, the eye with the worse BCVA letter score as assessed by ETDRS chart will qualify for the study eye;
- If both eligible eyes show the same size of CSFT and the same BCVA letter score, the eye with the clearer lens will qualify for the study eye;
- If both eyes show exactly the same conditions mentioned before, the investigator together with the patient may decide which eye will be selected as the study eye.

### 3.3.2 Inclusion criteria

1. Age  $\geq$  18 years
2. Male patients or female patients of non-childbearing potential 
3. Diagnosis of DM (type 1 or type 2) as evidenced by one of the following:
  - Current regular use of insulin for the treatment of diabetes
  - Current regular use of oral anti-hyperglycaemia agents for the treatment of diabetes
  - Documented diabetes by American Diabetes Association (ADA) and/or World Health Organization criteria
4. Retinal thickening due to DME involving the center of the macula in the study eye as confirmed by the Investigator on clinical exam
5. DME confirmed on SD-OCT with CSFT  $\geq$  300  $\mu$ m in the study eye at screening, confirmed by CRC
6. Best corrected visual acuity ETDRS letter score in the study eye  $\leq$  84 and  $\geq$  70 at screening
7. Media clarity, pupillary dilation and individual cooperation sufficient for adequate SD-OCT and fundus photographs
8. Signed and dated written informed consent consistent with GCP and local legislation prior to admission to the trial. Medication washout and medication restrictions are allowed only after signed informed consent is obtained.

### 3.3.3 Exclusion criteria

1. Macular edema considered to be due to other causes than DME in the study eye.

An eye should not be considered eligible if:

- The macular edema is considered to be related to ocular surgery, such as cataract extraction, or
  - Clinical examination and/or SD-OCT suggest that vitreoretinal interface abnormalities are contributing to the macular edema, such as a taut posterior hyaloid or epiretinal membrane
2. Additional eye disease in the study eye that, in the opinion of the Investigator, might affect macular edema or could compromise or alter visual acuity during the course of the study (e.g., vein occlusion, uncontrolled intraocular pressure (IOP)  $>$ 24 mmHg on

 Women of non-childbearing potential are defined as:

- postmenopausal ( $\geq$  12 months with no menses without an alternative medical cause) or
- permanently sterilized (defined as hysterectomy, bilateral oophorectomy or bilateral salpingectomy).

- optimal medical treatment, glaucoma with visual field loss, uveitis or other ocular inflammatory disease, vitreomacular traction, monocular vision, history of ischemic optic neuropathy, or genetic disorders such as retinitis pigmentosa)
3. Anterior segment and vitreous abnormalities in the study eye that would compromise the adequate assessment of the best corrected visual acuity or an adequate examination of the posterior pole
  4. An ocular condition is present in the study eye such that, in the opinion of the Investigator, any visual acuity loss would not improve from resolution of macular edema, e.g., foveal atrophy, dense subfoveal hard exudates, pigment abnormalities or fibrosis
  5. Intraocular surgery in the study eye within 4 months prior to randomization or planned intraocular surgery, including cataract, during the study period
  6. History of yttrium aluminium garnet (YAG) laser capsulotomy performed in the study eye within 2 months prior to randomization
  7. Proliferative diabetic retinopathy or iris neovascularisation (including the anterior chamber angle, ruled out by gonioscopy) in the study eye
  8. Aphakia in the study eye
  9. Any indication that requires immediate treatment or for which treatment is expected in the study eye with anti-VEGF or with laser photocoagulation during the course of the study, as per Investigator's judgment
  10. History of prior laser photocoagulation or other surgical, intravitreal or peribulbar treatment in the study eye within 4 months prior to randomization, either for DME or an ocular condition other than DME
  11. History of fluocinolone acetonide intravitreal implant in the study eye
  12. Application of intraocular corticosteroids in the study eye within 2 years prior to randomization in phakic eyes or 9 months in pseudophakic eyes
  13. History of topical steroid or nonsteroidal anti-inflammatory drugs (NSAID) treatment in the study eye within 30 days prior to randomization
  14. Systemic anti-VEGF or pro-VEGF treatment within 4 months prior to randomization
  15. Use of systemic steroids >10 mg prednisone equivalent/day within 4 weeks prior to randomization or known diseases which could require the use of such systemic steroids within the study period
  16. Current or planned, during the study period, use of medications known to be toxic to the retina, lens or optic nerve
  17. Initiation of intensive insulin treatment (multiple daily injections or a pump) within 3 months prior to randomization or plans to do so in the next 4 months
  18. Change in oral antidiabetic medication within 3 months prior to randomization
  19. Patients with a clinically relevant abnormal screening haematology, blood chemistry, or urinalysis, if the abnormality defines a significant disease as defined in other exclusion criteria; AST or ALT greater than 2.0-fold the upper limit of normal; Patients with total bilirubin (TB) or INR > 1.5x upper limit of normal. Laboratory testing may be repeated once during the screening phase
  20. Renal impairment with estimated creatinine clearance (CrCL; as calculated by Cockcroft-Gault equation) < 30 mL/min at screening, or where Investigator expects CrCL is likely to drop below 30 ml/min during the course of the study
  21. Myocardial infarction or unstable angina pectoris within 3 months before randomization

22. Uncontrolled arterial hypertension defined as a single measurement of systolic >180 mmHg, two consecutive measurements of systolic >160 mmHg, or diastolic >100mmHg on optimal medical regimen. If blood pressure is brought ≤160/100 mmHg by antihypertensive treatment, individual can become eligible
23. Significant disease or other medical conditions\* as determined by medical history, examination and clinical investigations at screening that may, in the opinion of the Investigator, result in any of the following:
  - Put the patient at risk because of participation in the study,
  - Influence the results of the study,
  - Cause concern regarding the patient's ability to participate in the study.

\*e.g. cardiac, gastro-intestinal, hepatic, renal, metabolic, dermatologic, neurological, haematological, oncological and psychiatric; history of relevant orthostatic hypotension, fainting spells or blackouts; current chronic or relevant acute infections including external ocular infections in the study eye such as significant blepharitis, chalazion or conjunctivitis; patients with malignancy for which the patient has undergone resection, radiation or chemotherapy within past 5 years. Patients with treated basal cell carcinoma or fully cured squamous cell carcinoma are allowed
24. Patients with a history of and/or active significant alcohol or drug abuse, as assessed by the Investigator
25. Known allergy to any component of the study drug
26. Women of childbearing potential or who are nursing
27. Male patients who do not agree to minimize the risk of female partners becoming pregnant from the first dosing day until 3 months after the trial medication treatment has finished
28. Patients who have participated in another investigational trial within the last 30 days preceding randomization with any drug that has not received regulatory approval or are participating in another trial (patients participating in a purely observational trial will not be excluded)
29. Previous randomization in this trial.

---

 Male patients who have sexual intercourse with women of childbearing potential will be instructed and must agree to use at least one of the following acceptable forms of effective contraception:

- Established use of oral, injected or implanted hormonal methods of contraception by the female partner of the male patient
- Placement of an intrauterine device (IUD) or intrauterine system (IUS) by the female partner of the male patient
- Use of barrier methods of contraception: Condom or Occlusive cap (diaphragm or cervical/vault caps) with spermicidal foam/gel/film/cream/suppository
- Sterilization of the male patient (with the appropriate post-vasectomy documentation of the absence of sperm in the ejaculate).

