#### 4.1.2 Method of assigning patients to treatment groups

During randomisation visit (Visit 2a) and after the patient's eligibility has been reconfirmed, the treatment will be assigned via Interactive Response Technology (IRT). To facilitate the use of the IRT, the Investigator will receive all necessary instructions.

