#### 5.3.4.1 Safety laboratory parameters obtained from blood

The laboratory parameters to be determined in this study are listed in [Table 5.3.4.1: 1](#) and will be performed by a central laboratory. Coagulation parameters will be collected at two visits together with other safety blood parameters. The respective reference ranges will be provided in the ISF. Regarding timing of sampling of safety blood markers please refer to the [Flow Chart](#), [Appendix 10.2](#) and to [Section 6.2](#).

Additional instructions for biomarker sampling, handling and shipment of samples are provided in the ISF.

The central laboratory will send reports to the Investigator. It is the responsibility of the Investigator to evaluate the laboratory reports. Clinically relevant abnormal findings as judged by the Investigator will be reported as adverse events (please refer to [Section 5.3.6](#)). In case the criteria for hepatic injury defined in [Section 5.3.6](#) (protocol-specified adverse events of special interest) are fulfilled, a number of additional measures will be performed (please refer to [Section 5.3.6](#) and DILI Checklist provided in the ISF). The amount of blood taken from the patient concerned will be increased due to this additional sampling. The central laboratory will transfer the results of the analysis to the sponsor.

Table 5.3.4.1: 1 Blood samples will be collected for the following tests in accordance with the visit [Flow Chart](#) and [Appendix 10.2](#):

Category	Test name
Chemistry	AST (GOT)
	ALT (GPT)
	Alkaline Phosphatase (AP)
	Creatine Kinase (CK)
	CK-MB, only if CK is elevated
	Gamma-Glutamyl Transferase (GGT/ $\gamma$ -GT)
	Lactic Dehydrogenase (LDH)
	Creatinine
	Creatinine clearance (CrCL) 
	Albumin
	Sodium
	Potassium
	Calcium
	Magnesium
	Chloride
	Inorganic phosphate
	Bicarbonate
	Bilirubin Total
	Bilirubin Direct, if total is elevated
	Bilirubin Indirect, if total is elevated
Protein, Total	
Uric Acid	
Glucose, non-fasting (fasting only at Visit 2a)	

Creatinine Clearance according to the Cockcroft-Gault formula

Table 5.3.4.1: 1 Blood samples will be collected for the following tests in accordance with the visit [Flow Chart](#) and [Appendix 10.2](#) (continued):

Category	Test name
Chemistry	HbA1c (only at Visit 2a and Visit 5/EOT) Total cholesterol (only at Visit 2a) LDL cholesterol (only at Visit 2a) HDL cholesterol (only at Visit 2a) Triglycerides (only at Visit 2a)

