Coagulation	Activated Partial Thromboplastin Time (=aPTT) (at Visits 2a and 5/EOT) Prothrombin time (Quick and INR) (at Visits 2a and 5/EOT)
Haematology	Haematocrit (Hct) Haemoglobin (Hb) Red Blood Cell Count/ Erythrocytes MCV (mean corpuscular volume) MCH (mean corpuscular haemoglobin) MCHC (Mean Cellular haemoglobin Concentration) Reticulocyte Count White Blood Cells / Leukocytes Platelet Count/ Thrombocytes
	Diff. automatic (manual if diff. automatic is abnormal) 
 
- Neutrophils
 
- Eosinophils
 
- Basophils
 
- Monocytes
 
- Lymphocytes
 

Urinalysis (Stix)	Urine Nitrite Urine Protein, semiquantitative; -> if abnormal, albuminuria will be determined quantitatively Urine Glucose Urine Ketone Urobilinogen Urine Bilirubin Urine RBC/ Erythrocytes Urine WBC/ Leukocytes Urine pH Urine creatinine

Table 5.3.4.1: 1 Blood samples will be collected for the following tests in accordance with the visit [Flow Chart](#) and [Appendix 10.2](#) (continued):

Category	Test name
Albumin content and Urine-Sediment, microscopic examination (both only if urine analysis abnormal)	Urine Albumin content Urine Sediment Bacteria Urine Cast in Sediment Urine Squamous Epith Cells Urine Sediment RBC/ Erythrocytes Urine Sediment WBC/ Leucocytes

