##### Visit 1 (Screening period):

The Screening period, i.e. the phase before the first administration of the trial drug, may be as long as 28 days but should be kept as short as possible. The minimum time interval between Visit 1 and Visit 2a is 2 days to allow receipt of the results of the central imaging Reading Center and the central laboratory.

Once DME is confirmed, a patient can be considered for eligibility; gonioscopy may be performed up to 1 month before study entry.

The screening period (see [Flow Chart](#)) includes the following procedures/assessments: check of signed Informed Consent, demographics, review of relevant medical history/baseline conditions at the discretion of the Investigator, current medication and relevant medication history regarding eye specific interventions (e.g., injection therapies, laser) within the last 2 years, inclusion/exclusion criteria, physical exam, body weight and height, vital signs (blood

pressure and pulse rate), ECG, safety laboratory tests collected according to central laboratory instructions, ophthalmological examinations including BCVA, slit lamp, SD-OCT, [REDACTED] and [REDACTED] ocular tonometry (intraocular pressure, IOP) and AE assessment since signed Informed Consent (see [Section 5.3.6](#)). Optional: Informed Consent for DNA banking; this separate consent can be obtained at this visit or at any other visit during the study.

In order to collect previous medical reports to keep records of exact dates/diagnoses of relevant medical history or prior medication, up to three documented attempts at different days should be made to get the reports before anamnestic data will be used.

Images (SD-OCT, [REDACTED]) have to be sent to the CRC for assessment immediately, see [Section 3.3.2](#). The Randomization visit 2a should be performed as soon as possible after the Visit 1, when eligibility of the patient was confirmed.

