#### **6.2.2 Treatment period**

The procedures of the visits in the treatment phase will be performed as outlined in the [Flow Chart](#).

As soon as eligibility of enrolled patients is confirmed, patients may enter the study and Visit 2a can be conducted including randomization via IRT. IRT should not be called in advance of Visit 2a, as randomization of a patient cannot be reserved.

SD-OCT and BCVA as well as blood sampling will always be performed before intake of the trial medication on the respective day.

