#### Visit 2a (Randomization)

At the start of Visit 2a it should be ensured that all Visit 1 procedures have been successfully completed within the past 28 days and eligibility has been confirmed including confirmation of eligibility by the CRC.

At Visit 2a (Day 1), patients need to have fasted overnight before this Visit until blood collection.

Visit 2a procedures include review of concomitant therapy, physical exam, body weight, vital signs (blood pressure and pulse rate), randomization, safety laboratory tests, PK, PGx (+

optional DNA banking sample, if Informed Consent is provided) and biomarker blood sampling collected according to central laboratory instructions (please also refer to [Appendix 10.2](#)), AE assessment since last visit (see [Section 5.3.6](#)), ECG and ophthalmological examinations including SD-OCT, visual acuity and slit lamp. Study medication should be taken after blood collection and ocular assessments at the site and study drug kits will be dispensed for home administration.

A trial drug diary will be provided to the patients to record the actual dates and times of drug administration prior to the next scheduled visit to keep records of missed drug intake and to take account of effects on PK trough levels.

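### Exclusion criterion 19 sets an INR limit, but INR is first scheduled at the randomization visit, so the result is unlikely to be known before randomization and first dose

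*Protocol*

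**What the plan says.** **The limit.** Criterion 19 in Protocol Section 3.3.3 deals with abnormal screening laboratory results. Besides AST and ALT limits, it excludes "Patients with total bilirubin (TB) or INR > 1.5x upper limit of normal". It allows laboratory testing to be repeated once in the screening phase.

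**The test schedule.** Table 5.3.4.1: 1 lists "Prothrombin time (Quick and INR) (at Visits 2a and 5/EOT"), and gives aPTT the same two visits. The text of Section 5.3.4.1 says the listed laboratory tests "will be performed by a central laboratory. Coagulation parameters will be collected at two visits together with other safety blood parameters".

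**The eligibility check.** Section 6.2.2 states: "As soon as eligibility of enrolled patients is confirmed, patients may enter the study and Visit 2a can be conducted including randomization via IRT". At the start of Visit 2a, sites must ensure that "all Visit 1 procedures have been successfully completed within the past 28 days and eligibility has been confirmed". Section 4.1.2 adds that "after the patient's eligibility has been reconfirmed, the treatment will be assigned via Interactive Response Technology (IRT"). The Flow Chart also places a review of the entry criteria at Visit 2a.

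**Timing.** Section 6.2.1 sets the minimum gap between Visits 1 and 2a at "2 days to allow receipt of the results of the central imaging Reading Center and the central laboratory". Table 10.2: 1 puts the Visit 2a safety sample at planned time -1:00 and the first dose at 0:00 on the same day.

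**The concern.** An exclusion limit works only if its result is in hand when the limit has to be applied. Here the first scheduled INR is drawn at the visit at which the patient is randomized and dosed, after the point at which eligibility should already be confirmed. A patient above the limit could therefore be randomized and take study drug before anyone knows the value.

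Once the result arrived, that patient could be recorded as a potential important protocol violation. Code A2 in SAP Table 6.2: 1 covers criterion 19 and excludes patients from no analysis set; the SAP describes the table as a working list. What is at stake is the safety purpose of the criterion and avoidable eligibility violations, not the primary CSFT comparison.

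**Working it through.** The documents give no figure to reproduce. The check sets the schedule against the eligibility rule and then compares the intervals.

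1. **INR tests scheduled before the randomization visit.** Section 5.3.4.1 gives two coagulation visits, 2a and 5/EOT. Neither precedes Visit 2a, so 0 of 2 scheduled INR samples can inform a decision due at the start of that visit. AST, ALT and total bilirubin carry no visit restriction in the table, and Table 10.2: 1 marks safety bloods at Visit 1. Of the numerical limits in criterion 19, only INR is affected.

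2. **Draw to first dose at Visit 2a** (Table 10.2: 1 and its footnote 2).
   - Nominal: 0:00 − (−1:00) = 1 h.
   - Earliest draw: 08:30 less the 30-minute tolerance = 08:00. Latest planned dose: 11:00.
   - Longest gap within these windows: 11:00 − 08:00 = 3 h (11:00 − 08:30 = 2.5 h without the tolerance).
   - The dosing window applies where possible, so 3 h is the planned maximum, not an absolute one. The IRT call comes before the dose, so less time is left for randomization.

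3. **Time the protocol allows for central results.** Section 6.2.1: at least 2 days = 48 h between Visit 1 and Visit 2a. This covers the reading center and the laboratory jointly, so it is not a laboratory turnaround. It supports, but does not prove, that a same-day central INR is unlikely.

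4. **Room for the permitted repeat.** A repeat needs a first result, a second draw and a second result. With 1 to 3 h between the first draw and the dose, the schedule makes no provision for this.

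5. **Other routes to a timely result.** No visible text provides a local INR, a same-day central report, or a hold on randomization until the Visit 2a INR arrives.

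6. **Number of patients above the limit.** This cannot be derived from the documents. It is probably small: Section 4.2.2.1 names warfarin among the drugs not permitted from 4 weeks before first dose, and criterion 23 excludes significant hepatic or haematological disease in the investigator's opinion.

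**The case against.** The strongest reply has five parts.

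- **Hidden text.** The Flow Chart footnote on safety blood tests is redacted, Table 10.2: 1 is visible only to Visit 3, and the laboratory manual is not available. Any of these might add INR at Visit 1. That is possible, and it is why the point rests on the visible text. However, the Visit 1 and 2a rows of Table 10.2: 1 are visible, and a Visit 1 INR would make three coagulation visits where Section 5.3.4.1 says two, so a correction would still be needed.
- **Wording.** The HbA1c and lipid rows of the table say that the test is done only at the named visits; the coagulation rows do not. This is fair as to the table alone, but the sentence counting two visits closes the gap.
- **Definition of screening.** Section 6.2.1 describes screening as "the phase before the first administration of the trial drug", so a pre-dose Visit 2a sample nominally falls within it. This stands. It settles when the sample may be drawn, not when the result is known.
- **Turnaround.** None is stated, and the 2 days are a joint allowance. This also stands: the claim is that a timely result is unlikely, not impossible.
- **Existing gate.** A patient with unknown INR is arguably not confirmed eligible, so randomizing that patient would breach the protocol. But the gate can use only results in hand, and the schedule supplies none. Read strictly, it could not be passed at the start of Visit 2a on scheduled tests alone. Section 8.3.1 lets investigators seek earlier test evidence, but it neither requires nor schedules an INR.

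**Conclusion.** The concern holds on the visible text. Criterion 19 carries an INR limit for which no scheduled result can be expected before randomization and first dose, and the repeat it permits has no place in the schedule. The gap from draw to dose is 1 h nominally and about 3 h at most within the stated windows, against a joint allowance of 48 h for central results.

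The conclusion assumes that the redacted footnote and the laboratory manual do not provide an earlier or same-day INR. The documents do not show whether the criterion or the table is in error. Few patients are likely to be affected. The point should be corrected because it concerns a stated safety exclusion and the correction is cheap.

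**What to change.** Reconcile Protocol Sections 3.3.3 (criterion 19), 5.3.4.1 with its table, and 10.2 so that any INR limit used for eligibility has a scheduled result before the IRT call. One example, leaving the limit unchanged, is to run coagulation on the safety blood already drawn at Visit 1, either in addition to the Visit 2a sample or in place of it. SAP 7.8.2 accommodates both, because laboratory baseline is the last available value before study drug.

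**Cost.** An amendment to the sampling tables and the laboratory manual, with no extra visit or blood draw. The documents give no screen-failure rate; assume 30% to 50% for 100 randomized patients:

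- Screened: 100/(1 − 0.30) = 143 to 100/(1 − 0.50) = 200.
- Visit 1 added, Visit 2a kept: about 143 to 200 more coagulation tests.
- Visit 1 in place of Visit 2a: 143 − 100 = 43 to 200 − 100 = 100 more tests. The coagulation baseline could then be up to 28 days before first dose, and the same-day pre-dose value would be lost.

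Permitted repeats and re-screening tests come on top in both cases.
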